25.0 Setting

Research will take place within Children's Mercy Adele Hall campus and the Children's Hospital of Philadelphia. Most of the study procedures will be conducted in the emergency department.

26.0 Resources Available

Providers: Study team members and leaders will be readily available by email and in-person to resolve any issues that arise. The leadership teams representing the ED Providers also support this project and are available to provide assistance if needed.

Adolescents: Participants are not required to answer questions that make them feel uncomfortable. In the emergency department, there are always advocates available for patients and families, if needed, including health care providers, social workers, and patient advocates. In this study setting, if a participant expresses a concern or need that is outside of the scope of this project (e.g., sexual assault), we will refer those participants back to their ED treating team, as is our standard practice. During the consent process, we will inform participants that most of the information they share during the study will be kept confidential except in rare cases where their safety is at risk or mandated reporting is in effect.

27.0 Multi-Site Research

Drs. [name] and [name] have a detailed plan for study oversite that was reviewed and approved by the NIH. Communication between study sites will take place via conference calls and emails. Regular conference calls will take place to discuss study updates, discuss any potential barriers and concerns and discuss other study logistics. Our estimated recruitment plan is detailed in the table below.

	CMH	CHOP	Total
Providers	Approximately 30	Approximately 30	60
Adolescents	49	49	98
Other personnel	15	15	30
Total	74	74	158

## Statistical analysis plan

We used R software (R Foundation for Statistical Computing) for analyses. In keeping with guidance discouraging the use of “statistical significance” and binary hypothesis testing based on arbitrary cutoffs (e.g.,  $P < .05$ ), we examined effect sizes along with  $P$  values and include  $P$  values without describing them as “significant” or “not significant.” Consistent with this approach, we did not attempt to control the familywise error rate (probability of at least one type I error across the study), which is not defined outside of binary hypothesis testing. We summarized closed-ended feasibility outcomes using descriptive statistics. We used an intention-to-treat analysis to assess preliminary efficacy and Fisher exact tests to compare arms on the percent of participants using contraception at 30 days. Dropouts during the index visit were treated as having no subsequent contraceptive use. Differences in average change score (e.g., attitudes) between arms were tested using nonparametric permutation tests.

*Primary Outcome:* We hypothesized the intervention would be deemed feasible by stakeholders. Drawing on similar examples in the literature, we determined a priori that the intervention would be feasible if the mean score across five Likert-scale survey items was  $\geq 4$  (range 1-5).

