2.0 Objectives

Evaluate intervention feasibility constructs: acceptability, demand implementation, practicality, adaptation, integration, expansion, and limited-efficacy. We will conduct a small randomized trial to assess feasibility and use mixed-methodology to explore contextual factors at the patient, provider, and system levels. In evaluating limited-efficacy, we compare two arms (MLI vs. eSOC) to determine size of effect rates on contraception initiation.

Hypothesis 1.1: The intervention will be deemed feasible by stakeholders: adolescents and organizational personnel (i.e., study providers, adolescent medicine specialists, hospital nursing and administrative leaders).

Hypothesis 1.2: Adolescents in the MLI arm will have greater contraception initiation rates relative to the eSOC arm at 30 days after the index ED visit.

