4.0 Study Endpoints

The primary endpoint will be the determination of feasibility. Methods for establishing feasibility vary and include levels of acceptability, satisfaction, or usefulness. Drawing on similar published criteria, the intervention will be deemed feasible if the average score across all items is ≥ 3 on closed-ended survey items for adolescents, providers, and OOPs (Table 1).

Secondary endpoints will include the following:

- The completion of a referral for any contraceptive care as assessed through EMR review or follow-up phone calls.
- The initiation of contraception as assessed through EMR review or follow-up phone calls.
- Saturation of themes from qualitative interviews that have been coded and analyzed.

Hypotheses 1.1 and 1.2: To establish feasibility, we assess multiple constructs via survey items among all stakeholders (Table 1).

Hypotheses 1.2: We will determine referral completion and date for contraception initiation (Time 0) via participant contact and review of study/medical records at thirty days after the index visit.

Table 1: Mixed-Methodology Feasibility Assessment with Adolescent and Personnel Stakeholders

Construct	Source	Index Visit: Post-intervention	Time from Index Visit	Time from Initiation (Time 0)		
			30 Days*	3 mos*	6 mos*	
Acceptability - How do stakeholders react to the intervention?	Adolescent	S	S	S	S	
	Providers	S			SSI	
	Other personnel				S, SSI	
Demand - To what extent is the innovation likely to be used?	Providers				S, SSI	
	Other personnel				S, SSI	

SHORT TITLE: Reducing Pregnancy in the ED

	Study/Medical Record*				SMRR
Implementation - To what extent can the intervention be implemented as planned (including intervention fidelity)?	Providers	S			SSI
	Other personnel				S, SSI
	Study/Medical Record*	SMRR	SMRR		
Practicality - What factors make intervention delivery challenging or facilitate delivery?	Providers	S			S, SSI
	Other personnel				S, SSI
	Study/Medical Record*				SMRR
Adaptation – How does model perform in new setting?	Providers				SSI
	Study/Medical Record*				SMRR
Integration - To what extent can model be integrated within the system?	Providers				S, SSI
	Other personnel				S, SSI
Expansion - To what extent can model be expanded to provide service?	Providers				S, SSI
	Other personnel				S, SSI
	Study/Medical Record*				SMRR
Limited efficacy testing - What are rates of contraception initiation/continuation and referral completion?	Adolescent		S	S	S
	Study/Medical Record*	SMRR			SMRR

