Prior to adolescent patients being enrolled, providers will be enrolled to participate in the study. Providers will be trained on motivational interviewing practices, contraception methods, as well as medication ordering practices.

Research team staff will screen potential study candidates via electronic tracking board. The research team will approach patients to ensure that they meet qualifications for the study. If qualifications are meet, the research team will provide consent/assent to the patient, conduct a pre-counseling survey, then notify a study provider of study status. Once the subject has been enrolled, the study provider will provide contraception counseling, while incorporating motivational interviewing techniques. Counseling sessions will be audio recorded and analyzed periodically for fidelity. At the completion of counseling, the study provider will offer the participant various contraception options and incorporate warm-referral practices to encourage follow-up at a local health clinic. The subject and provider will complete the Adolescent Post-Counseling Survey via REDCap at the end of their initial enrollment .

Immediately after the initial enrollment and at thirty-days post intervention, the research team staff will conduct a medical chart review. At thirty days, three months and six months post-intervention, a follow-up survey will be sent to the participant. OOP and provider staff will participate in semi-structured interviews that can be completed either in-person, virtually, or via telephone at 6-months to evaluate the feasibility of the study.

6.2

To help ensure the safety and validity of this study, we will ensure that provider staff are properly trained prior to enrollment. Training sessions will cover interviewing techniques, contraception, and ordering practices.

Members of the study team will also review audio recordings periodically for intervention fidelity.

6.3

Prior to approaching an adolescent participant, research team members will view the medical chart to ensure eligibility. Team members will look for the following, date of birth, custody status, and current contraception usage. In the post-intervention medical chart review, team members will look to see if a follow-up visit had been completed, and if so, if any services were obtained.

Surveys from adolescent participants will assess attitudes towards contraception, pregnancy prevention methods, perceived risk of contraception, and barriers to follow-up care.

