
6.4

SHORT TITLE: Reducing Pregnancy in the ED

Enrolled adolescents will receive follow-up surveys at 30-days, 3-months, and 6-months after their initial enrollment at their ED visit. The questions asked will assess subjects' attitudes towards contraception methods, access to care, and contraception efficacy. Enrolled patients may complete the survey over the phone with a member of the research team. A link may also be sent via text messaging using Twilio or other approved messaging system or to their email address.

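### Adjusting follow-up survey scores for the pre-counselling score would be more precise than testing raw change, at no cost; the 30-day comparison should also carry a risk difference with a 95% interval

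*SAP*

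**What the plan says.** **Survey scores.** The SAP (Statistical analysis plan) states: "Differences in average change score (e.g., attitudes) between arms were tested using nonparametric permutation tests". It names no baseline covariate. Protocol section 6.0 has research staff "conduct a pre-counseling survey, then notify a study provider of study status", so a score from before counselling exists. Section 6.3 says: "Surveys from adolescent participants will assess attitudes towards contraception". Section 6.4 has the follow-up surveys at 30 days, 3 months and 6 months cover "attitudes towards contraception methods, access to care, and contraception efficacy". The SAP does not say which follow-up survey supplies the change score. Attitude change is not among the endpoints in section 4.0.

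**30-day use.** The SAP uses "Fisher exact tests to compare arms on the percent of participants using contraception at 30 days" under intention to treat. It says of its approach that "we examined effect sizes along with" P values, but it names no effect measure for this outcome and plans no confidence interval; the protocol gives neither. Section 2.0 states the purpose: "we compare two arms (MLI vs. eSOC) to determine size of effect rates on contraception initiation". Section 4.0 lists as a secondary endpoint: "The initiation of contraception as assessed through EMR review or follow-up phone calls".

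**Previous use.** The randomization paragraph (C6eii, in section 6.0) says previous contraceptive use may influence uptake and that blocks of 4 or 8 are meant to balance it between arms. It does not make clear whether blocks ran separately within previous users and others. The SAP does not use previous use in any analysis.

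**The concern.** A change score subtracts the baseline with a fixed weight of 1. When the correlation between the two measurements is moderate, that weight is too large, and noise from the baseline passes into the comparison. Estimating the weight by regression removes this noise. With 98 adolescents (Protocol 1.0), intervals are wide and precision that needs no new data is worth taking.

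For 30-day use the matter is one of reporting. The SAP sets aside significance cut-offs and the protocol wants the size of an effect, yet the only inferential result specified is a P value. A P value does not show which differences remain compatible with the data.

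**Working it through.** The documents give no SD, correlation, target rate or power for these comparisons, so there is no stated figure to reproduce. Every such value below is an assumption.

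**1. Inputs from the documents.** N = 98 (Protocol 1.0) at 1:1 (C6eii), so 98/2 = 49 per arm. The 49/49 split in section 1.0 is by site.

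**2. Survey scores, equal SDs.** In units of one SD, with n per arm and pre–post correlation ρ:
- variance of the difference in mean change: 4(1−ρ)/n
- variance of the baseline-adjusted difference: 2(1−ρ²)/n
- ratio, adjusted to change: (1+ρ)/2

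The 95% half-width is the t quantile times the square root. Worked case, ρ = 0.5, n = 49: change 1.985 × √(2/49) = 0.401; adjusted 1.985 × √(1.5/49) = 0.347.

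| ρ (assumed) | Variance ratio | Half-width, 49 per arm (SD) | Half-width, 39 per arm (SD) |
|---|---|---|---|
| 0.3 | 0.65 | 0.475 → 0.383 | 0.534 → 0.430 |
| 0.5 | 0.75 | 0.401 → 0.347 | 0.451 → 0.391 |
| 0.7 | 0.85 | 0.311 → 0.286 | 0.349 → 0.322 |

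The 39 per arm supposes 80% follow-up.

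**3. Unequal SDs.** With k = follow-up SD / baseline SD, the ratio is (1−ρ²)k² / (k² + 1 − 2ρk). For ρ = 0.3, 0.5, 0.7 it is 0.50, 0.57, 0.63 at k = 0.8 and 0.78, 0.89, 0.98 at k = 1.25. It reaches 1 when ρk = 1, that is, when the regression slope is itself 1; there the two analyses coincide and nothing is gained.

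**4. Validity.** In simulation at 49 per arm (4,000 runs per setting, t-based tests standing in for permutation), type I error was 4.0% to 5.1% for change scores and 4.3% to 5.0% for baseline adjustment. For skewed 5-point scores (3,000 runs, 199 permutations, latent ρ of 0.3, 0.5, 0.7), the variance ratios were 0.64, 0.73, 0.81. The adjusted 95% interval covered 95.2%, 94.8%, 95.6%, and permuting the adjusted difference gave P ≤ 0.05 under no effect in 5.0%, 5.0%, 4.5% of runs.

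**5. 30-day use.** For illustration take 11/49 in the control arm (22.4%, borrowed from the 22% referral completion in Protocol 3.0, which is not a design assumption) and invent the intervention counts. Intervals are Newcombe's.
- 11/49 vs 23/49: Fisher P = 0.019; difference 12/49 = 24.5 points, 95% CI 5.6 to 41.1.
- 11/49 vs 17/49: Fisher P = 0.26; difference 6/49 = 12.2 points, 95% CI −5.6 to 29.1.

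In the second case the P value alone hides that a 29-point benefit is still compatible with the data.

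**6. Stratifying by previous use.** Simulation with N = 98, 22% vs 47% (a 25-point arm difference), 50% previous users and blocks of 4 or 8, all but N and block sizes assumed. The shift is the gap in 30-day use between previous users and others. Mean 95% interval widths in points, Miettinen–Nurminen for both crude and stratified (500 runs each):

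| Shift | Blocks within previous use: crude → stratified | Not within: crude → stratified |
|---|---|---|
| 10 | 35.7 → 35.6 | 35.8 → 35.8 |
| 25 | 35.8 → 34.6 | 35.7 → 34.8 |
| 40 | 35.8 → 32.6 | 35.7 → 32.7 |

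The sampling variance of the estimate is a separate matter. Stratified relative to crude (8,000 runs), it is 1.00, 1.00, 0.99 with blocks within previous use and 1.00, 0.92, 0.81 without.

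**The case against.** The strongest reply is that a permutation test of mean change is valid, simple and answers a direct question: did one arm change more? It concerns an outcome outside the endpoint list, no precision target is set for it, and the feasibility decision rests on mean survey scores. The gain depends on a correlation that the documents do not give and falls to 2% of the variance in one of the cases above. All of this stands, and it is why the point is minor. It does not remove the advantage: the ratio was below 1 in every setting tried, and the change costs nothing.

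On 30-day use, the SAP already promises effect sizes and speaks of percentages, so a difference in percent is the natural reading. That also stands. What is left is mostly missing detail: the measure is not named and no interval is planned.

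Three stronger readings are tempting, and the documents support none of them.
- A reader might infer that the change-score test is biased or has the wrong error rate. Under randomization it does not.
- A reader might infer that leaving previous use out makes Fisher's test invalid. It stays valid, and C6eii states an intent to balance previous use, not to stratify the analysis by it.
- A reader might infer that stratifying costs width when previous use is weakly prognostic. That appears only if a stratified Miettinen–Nurminen interval is set against a crude Newcombe interval (about 35.1 points). With one method for both, the widths at a 10-point shift are essentially equal.

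**Conclusion.** This is a free improvement to an exploratory analysis, not an error. Baseline adjustment would have 0.65 to 0.85 of the change-score variance for ρ between 0.3 and 0.7 with equal SDs, and 0.50 to 0.98 over the unequal SDs tried. At ρ = 0.5, 98 participants analysed by change carry about the information of 98 × 0.75 ≈ 74 analysed with adjustment. These figures assume a linear relation and a pre-counselling score unaffected by arm.

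The 30-day point is secondary: an interval is needed to serve the stated aim of sizing the effect. Stratifying by previous use is optional. On the assumptions above it leaves the mean width essentially unchanged at a 10-point shift and narrows it by about 0.9 to 1.2 points at 25 and about 3 points at 40. If blocks ran within previous use, the estimate itself is no less variable, and the narrowing only removes excess width from the crude interval. If they did not, sampling variance also falls, by about 0 to 19%. The primary feasibility outcome is untouched.

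**What to change.** 1. **Survey scores.** Report the arm difference in follow-up score adjusted for the pre-counselling score, with a 95% confidence interval, and say which follow-up survey is used. Keep the permutation test: permute the arm labels and take the adjusted difference as the statistic.
2. **30-day use.** Name the risk difference as the effect measure and report it with a 95% interval. Fisher's test can stay as the source of the P value.
3. **Optional.** Beside the crude difference, give one stratified by previous use (Mantel–Haenszel weights, stratified Miettinen–Nurminen interval), with the crude interval by the same method so that the two compare fairly. State whether blocks ran within previous use.

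The cost is a few lines of R and of SAP wording, with no new data. The SAP is written in the past tense, so anything added after the analysis should be labelled post hoc.
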